### 5.3.5 Parental atopic medical history

Parental (father and/or mother) atopic history is recorded on the Parental Atopic History eCRF page and will be summarized as the number and percentage of subjects with father / mother having any of the following conditions:

- asthma,
- seasonal allergies,
- perennial allergies,
- food allergies,
- eczema/atopic dermatitis,

CONFIDENTIEL / Ne pas diffuser sans autorisation de DBV

CONFIDENTIAL / Do not distribute without DBV authorization

	Statistical Analysis Plan	
	EPITOPE (V712-304) – Statistical Analysis Plan	
	Référence du Document /Document Reference : CCI [REDACTED]	Page : 30 / 74

CCI [REDACTED]

- other allergic diseases.

The number and percentages of subjects with at least one parental atopic medical history will also be provided.

Parental atopic medical history will be summarized overall and by treatment group for the Safety set. Parental atopic medical history data will be also provided in listings.

In case a subject's parent is not the biological parent, no parental medical history is collected about this parent.

### 5.3.6 Disease history

Disease history covers the collection of information about the peanut allergy of the subject and will be reported using the following characteristics:

- Age at peanut allergy diagnosis (in months, calculated as  $12 * (\text{Date of diagnosis} - \text{Date of birth}) / 365.25$ ),
- Time since peanut allergy diagnosis (in months, calculated as  $12 * (\text{Date of Informed consent} - \text{Date of diagnosis}) / 365.25$ ),
- Category of the physician who made the diagnosis,
- Main reason having led to the diagnosis (reaction after ingestion, parental/sibling history of atopy, other risk factors)
- Diagnosis criteria (Allergic reaction(s) following peanut consumption, Positive SPT to peanut, Positive titer of peanut-sIgE, Positive Double-Blind Placebo-Controlled FC to peanut, Positive Single-Blind Placebo-Controlled FC to peanut, Positive Open FC to peanut)
- Most recent results of peanut allergy diagnostic tests performed,
- Description of allergic reactions:
  - Number of allergic reactions after ingestion of peanut,
  - Number of allergic reactions after ingestion of peanut in the previous 12 months,
  - Time since last reaction after ingestion of peanut (in months, calculated as  $12 * (\text{Date of Informed consent} - \text{Date of last reaction}) / 365.25$ ). When the date of last reaction is partial (only year available or year and month), the latest possible date will be assumed (e.g. 31st of December or last day of the month).
  - Allergic reaction after ingestion of peanut after the age of 2 years old.

When the date of diagnosis is partial (only year available or year and month), the latest date between the date of birth and the earliest possible date of diagnosis (e.g. first of January or first day of the month) will be considered.

Disease history will be summarized by treatment group and overall for the Safety set. Disease history data will be also provided in data listings.

CONFIDENTIEL / Ne pas diffuser sans autorisation de DBV

CONFIDENTIAL / Do not distribute without DBV authorization

	Statistical Analysis Plan	
	EPITOPE (V712-304) – Statistical Analysis Plan	
	Référence du Document /Document Reference : CCI	Page : 31 / 74

CCI

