## 5.2.6 Key dates, Relative days

### 5.2.6.1 Key dates

- **The date of first patch application** of each subject will be taken from the first exposure date from eCRF.
  - If only the day is missing, it will be imputed using the day of the latest date between the randomization date and the first dispensation date.
  - If day and month are missing, they will be imputed using the day/month of the latest date between the randomization date and the first dispensation date.
  - If the date is missing, it will be taken from first dispensation date.
- **The date of last patch application** of each subject will be taken from the last exposure date from eCRF.
  - If only the day is missing, it will be imputed to the last day of the month unless month and year are the same as month and year of study end date then impute study end date

CONFIDENTIEL / Ne pas diffuser sans autorisation de DBV

CONFIDENTIAL / Do not distribute without DBV authorization

	Statistical Analysis Plan	
	EPITOPE (V712-304) – Statistical Analysis Plan	
	Référence du Document /Document Reference : CCI	Page : 24 / 74

CCI

- If day and month are missing, they will be imputed to the 31st of December unless year is the same as year of study end date then impute study end date.
- If the date is missing because the subject was lost to follow-up, it will be derived from the study end date.
- **The study end date** will be derived as the study completion date or study discontinuation date from the disposition domain.
- If the date is missing, it will be derived as the last date available from the visits, the examination, the assessments.

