**AE end date**

- If AE end date is missing or AE is ongoing, the AE end date will not be imputed.
- If AE end date is partial:
  - If AE end day is missing, it will be imputed to the earliest date (last day of the month/Month AE end/Year AE end, death date)
  - If AE end day and month are missing, they will be imputed to the earliest date (31DEC/Year AE end, death date)

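### A partial date of last peanut reaction is set to the latest possible date with no cap at consent, so a year-only date in the consent year gives a negative time since last reaction

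*SAP*

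**What the plan says.** SAP 5.3.6 (Disease history) lists the variable as "Time since last reaction after ingestion of peanut (in months, calculated as" 12 times the consent date minus the date of last reaction, divided by 365.25. The partial-date rule follows directly: "When the date of last reaction is partial (only year available or year and month" are both covered, and in either case "the latest possible date will be assumed (e.g. 31st of December or last day of the month".

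The same section treats a partial diagnosis date differently. It takes "the latest date between the date of birth and the earliest possible date of diagnosis", so the imputed diagnosis cannot precede birth.

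On use, the section says: "Disease history will be summarized by treatment group and overall for the Safety set". The data are also listed by subject.

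**The concern.** Consent and disease history both belong to Visit 1 (Protocol 7.2.1), and the history comes from the parents or the medical records (Protocol 6.3.2). A past reaction recorded there should not be dated after consent. The rule nevertheless moves a partial date to the end of its year or month without checking that this comes before consent. For a partial date in the consent year or consent month, the formula then returns a negative duration.

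At stake is the accuracy of one row in the baseline tables. The reported minimum can be impossible, and the mean is pulled below what a bounded rule would give. There is also room for inconsistent programming: one programmer might cap the date, another keep the negative values, and a third set them to missing, each with a different summary.

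Children enter at 1 to 3 years of age (Protocol 4.1), so reaction histories are short and a reaction in the calendar year of consent is plausible. How often such a date would be incomplete is not known.

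**Working it through.** The plan gives no figure of its own to reproduce. The check applies the SAP formula to its own imputation rule.

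**Inputs**
- Formula (SAP 5.3.6): T = 12 × (consent date − last reaction date) / 365.25, in months.
- Imputed reaction date (SAP 5.3.6): 31 December if only the year is known; last day of the month if year and month are known.
- Consent dates: illustrative, in a 365-day year (an assumption).

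**Year-only date in the consent year, imputed to 31 December**

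| Consent | Days from consent to 31 Dec | T (months) | T with cap at consent |
|---|---|---|---|
| 1 January | 364 | −12 × 364/365.25 = −11.96 | 0 |
| 31 March | 275 | −12 × 275/365.25 = −9.03 | 0 |
| 30 June | 184 | −12 × 184/365.25 = −6.05 | 0 |
| 15 October | 77 | −12 × 77/365.25 = −2.53 | 0 |
| 31 December | 0 | 0.00 | 0 |

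T is negative for 364 of the 365 possible consent days. If consent is spread evenly over the year (assumption), the mean T among these children is −5.98 months.

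**Year-and-month date in the consent month (March example)**
- Consent on the 1st: −12 × 30/365.25 = −0.99 months.
- Consent on the 15th: −12 × 16/365.25 = −0.53 months.
- Consent on the 31st: 0.

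**Dates the cap leaves alone**
- A year-only date in the previous calendar year with consent on 30 June gives 12 × 181/365.25 = 5.95 months, with or without the cap.

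**Is a bound given elsewhere?** The missing-date rules in SAP 5.2.4 deal with dates of birth and of findings, and refer to other sections for treatment, adverse-event and concomitant-medication dates. Disease-history dates are not among them. Comparable rules in the SAP do state their bounds:
- Partial diagnosis date (5.3.6): floor at the date of birth.
- Partial date of last patch (5.2.6.1): "it will be imputed to the last day of the month unless month and year are the same as month and year of study end", in which case the study end date is used.
- Partial adverse-event end date (5.5.1.2): "it will be imputed to the earliest date (last day of the month/Month AE end/Year AE end, death date", that is, capped at death.
- Partial assessment date (5.2.4): the visit date is used when the known parts agree with it.

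SAP 5.3.8 also sets a negative patch-wear duration to missing as aberrant. No such safeguard covers time since last reaction.

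**The case against.** The strongest reply is that the word *possible* already carries the bound. A reaction reported at the consent visit cannot have happened later, so the latest possible date is never after consent, and 31 December and month-end are only examples. This reading is available but cannot be relied on. The examples are unqualified, and the companion rule for diagnosis also speaks of a possible date yet still writes out its floor at birth.

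A second reply concerns reach. The large negative values need a reaction in the consent year *and* a date known only to the year. A reaction known to an earlier month is unaffected, and one known to the consent month is off by at most about 1 month. Parents may well recall the month of a recent reaction. Some children will have no prior reaction at all, because Protocol 4.1 admits on high suspicion. All of this stands: the frequency is unknown and may be low.

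Third, nothing inferential depends on the variable. It is not an eligibility criterion, a subgroup factor (SAP 5.2.5), or a covariate in the primary imputation model or the ED and CRD analyses (SAP 5.4.1 and 5.4.2). A negative value would also be obvious in the subject listing. This stands too, and it is why the point ranks as minor.

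Last, a cap puts every affected child at 0 months and leaves some downward bias. Suppose reactions fall evenly between 1 January and a 30 June consent. The true mean is then about 3 months (half of 180 days, 12 × 90/365.25 = 2.96), against −6.05 under the current rule and 0 under the cap. The remaining bias is real, but it comes from the latest-date convention itself. The cap moves every affected value closer to the truth, so it costs nothing relative to the rule as written.

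**Conclusion.** The concern holds. Followed as written, SAP 5.3.6 produces negative times since last reaction: between 0 and about −12 months for a year-only date in the consent year, and between 0 and about −1 month for a year-and-month date in the consent month. No other SAP rule prevents this.

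The per-child figures rest only on the SAP formula and calendar arithmetic. The effect on the reported mean depends on the share of partial dates, which the documents do not give. A single affected child is enough to make the reported minimum impossible. No efficacy or safety conclusion changes, so this is a desirable correction and not an essential one.

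**What to change.** Add one sentence to SAP 5.3.6: *if the imputed date of last reaction falls after the date of informed consent, the date of informed consent is used instead.*

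This keeps the sponsor's latest-date convention, makes 0 the smallest value an imputed date can give, leaves dates from earlier years unchanged, and brings the rule into line with the bounds written elsewhere in the SAP. The cost is that sentence and one line of code. A table footnote could say that imputed dates follow a latest-date convention, so that readers know a capped value is a lower limit for the interval.

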### 5.3.7 Prior and concomitant medications

All medications taken before the study entry, at study entry and during the study will be recorded and coded using the World Health Organization (WHO) Drug Dictionary (Sept. 2017).

Medications will be classified either as “Prior only” (P), “Both Prior and Concomitant” (PC) or “Concomitant only” (C).

This classification will be made by comparing the medication start and stop dates with the date of first/last application of study medication.

Medications starting after the completion/withdrawal date will be listed but will not be classified or summarized.

“Prior only” (P) medications will be:

- Medications that were taken within 6 months prior to the first dose of study medication and that stopped before the first dose of study medication,
- Medications with partial start/stop date where there is clear evidence to suggest that the medication stopped prior to the first dose of study medication.

“Both prior and concomitant” (PC) medications will be:

- Medications starting before the first dose of study medication and stops on or after the first dose of study medication,
- Medications with partial start/stop date where there is clear evidence to suggest that the medication started prior to the first dose of study medication (no evidence for the stop date).

“Concomitant only” (C) medications will be:

- Medications with a start date on or after the first dose of study medication,
- Medications with partial start/stop date where there is clear evidence to suggest that the medication started after the first dose of study medication,
- Medications with partial or complete stop date where there is clear evidence to suggest that the medication stopped after the first dose of study medication (no evidence for the start date),
- All other medications with partial start/stop date where there is no clear evidence to suggest that the medication started or stopped before or after the first dose of study medication.

In addition to the WHO Drug coding performed, the following medication classes are defined:

- Epinephrine,
  - They will be identified on PT that contains “EPINEPHRINE” and ATC level 1 = “CARDIOVASCULAR SYSTEM”.
- Systemic or inhaled corticosteroids,
  - They will be identified as:
    - Any medication ATC codes starting with “H02”

CONFIDENTIEL / Ne pas diffuser sans autorisation de DBV

CONFIDENTIAL / Do not distribute without DBV authorization

	Statistical Analysis Plan	
	EPITOPE (V712-304) – Statistical Analysis Plan	
	Référence du Document /Document Reference : CCI	Page : 32 / 74

CCI

- Any medication ATC code starting with “A07EA”, “C05”, “R01AD” and (ROUTE in “ORAL” “PO” “RECTAL” “RESPIRATORY (INHALATION)” “INTRAVENOUS”)
- Topical corticosteroids,
  - They will be identified as:
    - Any medication ATC code starting with “D07”
    - Any medication ATC code starting with “A07EA”, “C05”, “R01AD” and ROUTE = Topical.

For prior and/or concomitant medications, number and percent of subjects overall and per ATC class (level 3) and preferred drug name will be calculated. The following summaries will be presented overall and by treatment group for the Safety set:

- Prior medications (other than the ones taken during the food challenge at Baseline), prior only medications (P) will be taken into account;
- Concomitant medications (other than the ones taken for the food challenge at Month 12 and the ones taken for voluntary or accidental consumption of peanut), both prior and concomitant (PC) and concomitant (C) medications will be taken into account;
- Medications taken for food challenges, by time point;
- Concomitant medications taken due to accidental/voluntary consumption of peanut.

Number of antihistamine and number of epinephrine administrations during food challenges will also be tabulated separately (for the Peanut and Placebo days of DBPCFC separately), overall and by treatment group for the Safety set.

Non-drug therapies and surgical procedures are collected and will be coded using the version 20.1 of the MedDRA Dictionary. They will be also presented by SOC and preferred term overall and by treatment group for the Safety set.

All prior and concomitant medications, non-drug therapies and surgical procedures will be listed for the Safety set. The listing will be provided with a flag to indicate the prior and concomitant medications.

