### 5.5.1 Adverse Events

#### 5.5.1.1 Definitions

**Treatment-emergent AEs** will be defined as any AEs, regardless of relationship to IMP reported during or after the initial application, i.e. AEs where start date/time is on or after date/time of the first study treatment.

- When an AE's start date is equal to the date of first study treatment and the start time of AE is missing, AE will be defined as treatment emergent.
- Where dates are missing or partially missing, adverse events will be assumed to be treatment-emergent, unless there is a clear evidence (through comparison of partial dates) to suggest that the adverse event started prior to the first study treatment. More specifically, See Section 5.5.1.2.

AEs occurring after the end of the study will be recorded only if the investigator considers that there is a causal relationship with the IMP and as such, will be considered also as TEAEs.

**Pre-treatment emergent AE** will be defined as an AE that begins before the first administration of IMP.

**IMP-induced Local TEAEs** are defined as TEAEs considered as related to IMP with a High-Level Term equal to "Application and instillation site reactions" and will be flagged in the analysis datasets.

Following medication use will be defined:

- **Epinephrine use** will be identified by a combination of standard medication name that contains "EPINEPHRINE" and ATC level 1 = "CARDIOVASCULAR SYSTEM".
- **Systemic or inhaled corticosteroid use** will be identified by:
  - ATC code starting with "H02"
  - ATC code starting with "R03AK" (Adrenergics in combination with corticosteroids or other drugs, excl. anticholinergics) and "R03BA" (Glucocorticoids)
- **Topical corticosteroid use** will be identified by ATC code starting with "D07" (Corticosteroids, Dermatological preparations)

Treatment emergent adverse events of special interest (AESI), are defined as:

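### SAP 5.3.7 and 5.5.1.1 define the systemic-or-inhaled corticosteroid class with different ATC lists that share only H02, so class-level counts can disagree and the TEAE tables can miss steroid use

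*SAP*

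**What the plan says.** SAP 5.3.7 (Prior and concomitant medications) introduces its special classes with "In addition to the WHO Drug coding performed, the following medication classes are defined". One of them is "Systemic or inhaled corticosteroids". A record belongs to it if its ATC code starts with H02, whatever the route, or if it meets a second rule that combines code and route: "Any medication ATC code starting with “A07EA”, “C05”, “R01AD” and (ROUTE in “ORAL” “PO” “RECTAL” “RESPIRATORY (INHALATION)” “INTRAVENOUS".

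SAP 5.5.1.1 (Definitions, under Adverse Events) defines systemic or inhaled corticosteroid use again. Here the codes are H02, R03AK and R03BA, with no condition on route. The SAP glosses R03AK as "Adrenergics in combination with corticosteroids or other drugs, excl. anticholinergics" and R03BA as glucocorticoids.

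SAP 5.5.1.3 has two outputs that name this class: a row in the TEAE overview, and a table by system organ class and preferred term. The overview is repeated for the SAP 5.2.5 subgroups, with accidental peanut consumption included, and for the treatment period after the fourth birthday.

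The SAP 5.3.7 summaries cover all prior and concomitant medications by ATC level 3 and preferred drug name, and every medication is listed.

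**The concern.** One label carries two meanings. A product coded only to R03BA is an inhaled or systemic steroid in the adverse-event section but not in the medication section. A product coded only to R01AD and given by inhalation is the reverse. Neither SAP 5.11 (changes from the protocol) nor the modification history in SAP 7 mentions the difference. The epinephrine rule, by contrast, is essentially the same in both sections: a name containing epinephrine, plus ATC level 1 for the cardiovascular system. That suggests the paired definitions were meant to agree.

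What is at stake is a descriptive safety count. The need for systemic or inhaled steroids to treat an adverse event is a marker of how serious the reaction was, and the SAP tabulates it for that reason. Protocol 5.7.1 allows oral corticosteroids for allergic reactions, and Protocol 5.7.2 permits low-dose or short-course inhaled steroids, so some use during the study is to be expected. With two definitions in force, two programmers could both follow the SAP and report different counts.

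**Working it through.** No sample size, power or error rate bears on this point. The check is a comparison of two code lists, followed by a look at which planned outputs depend on each.

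**Step 1. The lists side by side**

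| ATC code | SAP 5.3.7 class | SAP 5.5.1.1 class |
|---|---|---|
| H02 | in, any route | in |
| A07EA, C05, R01AD | in, if route is oral/PO, rectal, inhalation or intravenous | out |
| R03AK | out | in, no route condition |
| R03BA | out | in, no route condition |

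In both: H02 only. Only in 5.3.7: A07EA, C05 and R01AD with the listed routes. Only in 5.5.1.1: R03AK and R03BA.

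**Step 2. The topical class**

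SAP 5.3.7 uses D07, plus A07EA, C05 and R01AD with topical route. SAP 5.5.1.1 uses D07 alone. The mismatch is of the same kind but runs one way only: the adverse-event list is the narrower.

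**Step 3. Outputs that rest on each definition**

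- The summaries planned in 5.3.7 (prior medications, concomitant medications, food-challenge medications, medications for peanut consumption) run over all drugs by ATC level 3 and preferred name. None is filtered by the corticosteroid class. An R03AK or R03BA product appears there under R03A or R03B and again by name.
- The TEAE overview row and the table by system organ class and preferred term in 5.5.1.3 do name the class, and the definition supplied for the adverse-event section is that of 5.5.1.1. These outputs therefore omit events treated only with A07EA, C05 or R01AD products given by a systemic or inhaled route.
- The same holds for the topical outputs in 5.5.1.3: an event treated with a topical product coded only to A07EA, C05 or R01AD is not counted.

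**Step 4. How many records**

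This depends on which ATC code or codes are stored for each medication record, which the documents do not state.

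- Lower end: if every steroid record carries a code found in both definitions, or if no child uses a product from the non-shared codes, nothing changes.
- Upper end for the TEAE tables: every event whose only systemic or inhaled steroid is coded solely to A07EA, C05 or R01AD is missed.
- Upper end for the 5.3.7 class: every product coded solely to R03AK or R03BA is outside it.

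The documents give no figure that narrows this range.

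**The case against.** The strongest reply is that nothing is lost. The 5.3.7 tables and listing include every drug, no output visible in 5.3.7 is built on the corticosteroid class, and the outputs that do name it have their own definition. On this view the difference is editorial. The first two parts stand, and they limit the point. The third does not dispose of it, because the definition that feeds those outputs leaves out products which the same SAP elsewhere calls systemic or inhaled steroids.

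Three stronger readings are tempting, and the documents support none of them.

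- A reader might infer that inhaled steroids drop out of the concomitant-medication tables. They do not: those tables are organised by ATC level 3 and drug name, without regard to class. Nor is 5.3.7 blind to inhaled use, since its second rule accepts an inhalation route. What an R03-coded product loses is membership of the class and any count of children built on it. The level-3 rows do not supply that count, because R03A and R03B are broader than R03AK and R03BA, and drug-name rows cannot be summed to children when one child may use several products.
- A reader might infer that use of a restricted medication is understated. Protocol 5.7.2 restricts moderate or higher daily doses and certain combinations, and permits low doses. Neither code list uses dose, so neither could identify a breach of the dose limit. Breaches are a matter for the protocol-deviation review in SAP 5.3.2.
- A reader might infer that the asthma subgroup is affected. It is defined in SAP 5.2.5 from ongoing medical history, using the MedDRA terms in SAP 5.3.4. Medication codes play no part.

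**Conclusion.** The inconsistency is real and runs in both directions. Two sections of the SAP define the same class with lists that share one code, and the adverse-event tables rest on a list that omits products which 5.3.7 assigns to the class. Class-level counts under one label can therefore disagree, and the count of TEAEs that led to systemic or inhaled steroid use can be too low.

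The size is unknown and may be nil. The conclusion assumes that the adverse-event outputs are programmed from the definition given in their own section and that some steroid records carry only one of the non-shared codes. It also assumes that no table shell or programming specification outside these documents already reconciles the two. The issue is confined to descriptive safety output; the primary and secondary efficacy analyses are unaffected. It is a minor correction, worth making because it is cheap and removes an ambiguity from a tabulated safety count.

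**What to change.** State one definition and refer to it from both SAP 5.3.7 and SAP 5.5.1.1:

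- **Systemic or inhaled corticosteroids:** H02; R03BA; R03AK limited to products that contain a corticosteroid; and A07EA, C05 or R01AD with an oral/PO, rectal, inhalation or intravenous route. The limit on R03AK is needed because the SAP's own gloss allows combinations with other drugs, so the code alone could bring in products without a steroid.
- **Topical corticosteroids:** D07; and A07EA, C05 or R01AD with topical route, in both sections.

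Derive each class once as a flag on the medication dataset and use that flag in every output. It would also help to say whether class membership is judged on all ATC codes stored for a record or on a single selected code, since that determines how much the two present lists differ in practice.

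The cost is a few lines of SAP text and a shared programming flag. No further data collection is needed, and no efficacy analysis changes.
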